5.15.1.11. Other Analyses

In addition, other analyses will be performed, allowing for adjustment of potentially confounding variables. Variables that may confound evaluation of a correlation between reversal of anti-fXa activity with effective hemostasis include anatomical location of bleeding, mechanism of injury (e.g., blunt vs. penetrating trauma; traumatic vs. spontaneous), severity of injury, severity of bleeding, presence and timing of interventions to stop bleeding (e.g., endoscopic cautery of bleeding ulcers, surgical ligation of bleeding vessel), and use of coagulation or hemostatic factors. These analyses will be defined later in an addendum to this analysis plan and will be labeled as post hoc in the clinical study report.

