In addition, other analyses will be performed, allowing for adjustment of potentially confounding variables. Variables that may confound evaluation of a correlation between reversal of anti-fXa activity with effective hemostasis include anatomical location of bleeding, mechanism of injury (e.g., blunt vs. penetrating trauma; traumatic vs. spontaneous), severity of injury, severity of bleeding, presence and timing of interventions to stop bleeding (e.g., endoscopic cautery of bleeding ulcers, surgical ligation of bleeding vessel), and use of coagulation or hemostatic factors. Assessment of various parameters of prediction of clinical hemostasis will also be considered, including a threshold of anti-fXa activity, a percent reduction in anti-fXa activity, and an absolute reduction in anti-fXa activity.

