5.4. Adjustment for Covariates

No adjustment for covariates will be performed.

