5.14. Secondary Efficacy Analysis

The secondary objective of the study is to assess the relationship between the change from baseline in anti-fXa activity and achievement of hemostatic efficacy in patients receiving an FXa inhibitor who have acute major bleeding and reduced FXa activity.

Analysis

A logistic regression model predicting the log-odds ratio of success of hemostatic efficacy (rated as "Excellent" or "Good"), with the anti-fXa level activity as a covariate will be used to determine the relationship between anti-fXa level and the clinical outcome.

A subset analysis on the Intracranial patients will be performed using a logistic regression with 2 additional covariates: the log of (the baseline ICH volume + 1), and an indicator variable for baseline Infratentorial involvement.

Anti-fXa Level Measurement

Hemostatic efficacy is achieved when the body has time to produce thrombin and a subsequent clot, thus the anti-fXa level during the first few hours after administration is more important than the decrease in anti-fXa level to predict the log-odds of success of hemostatic efficacy. Therefore, the on-treatment nadir value will be used in the analysis.

Standardization Across Inhibitors

The most power would be gained if it were possible to pool the data across all the anti-fXa inhibitors, however, anti-factor Xa activity levels cannot be combined in the same analysis due to the different bioavailability and pharmacokinetics of the individual FXa inhibitors, especially between the direct and indirect FXa inhibitors. An alternative way to use the activity level that would enable pooling the data is to convert the continuous measurements into a dichotomous variable indicating a level that has similar anticoagulant effects across the 4 different inhibitors.

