For the DOACs, current guidelines by the subcommittee on control of anticoagulation of the International Society on Thrombosis and Hemostasis (ISTH) and the French Working group on perioperative hemostasis (GIHP) recommend using a value of 30 ng/mL to determine if antidote administration should be considered.[4, 5] Unfortunately there is no similar threshold for the indirect anticoagulants, therefore the threshold for the Enoxaparin patients in the analysis will be the lower limit of detection (0.10 IU/mL). Sensitivity analyses excluding patients taking Enoxaparin will be performed as well, with (1) the log of anti-fXa at on-treatment Nadir as a covariate, and (2) the dichotomous variable for anti-fXa less than the threshold as a covariate.

A summary of the planned analyses is below:

Model	Population	Reduced Model covariates	Full Model covariates
1	Efficacy, excluding patients with Non-Evaluable Hemostatic Efficacy due to Admin reason	None (intercept only model)	Indicator variable for on- treatment Nadir anti-fXa level < threshold*
2	Same as (1) except exclude Enoxaparin patients also	None (intercept only model)	Indicator variable for on- treatment Nadir anti-fXa level < threshold*
3	Same as (1) except exclude Enoxaparin patients also	None (intercept only model)	Log of on-treatment Nadir anti-fXa level

4	Same as (1) except exclude non-ICH patients also	Log of (baseline ICH volume +1), Indicator	Reduced Model covariates plus Indicator variable for
	non-reri patients also	variable for Infratentorial	on- treatment Nadir anti-
		involvement	fXa level < threshold*

^{*}The threshold=30 ng/mL for Apixaban, Rivaroxaban and Edoxaban, and 0.10 IU/mL for Enoxaparin.

Descriptive statistics, odds ratios with the corresponding 95% confidence intervals, and p-values from the models will be presented. The Full Model will be compared to the Reduced Model with a Likelihood Ratio Test. The Reduced Model will be rejected in favor of the Full Model if the Likelihood Ratio Test p-value is <0.05.

The area under the receiver operating characteristic (AUC under ROC) with the 95% CI will be presented.

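### SAP 5.14 Models 1–3 test the anti-fXa nadir with no baseline covariate, so an association could reflect baseline level, inhibitor or bleed type rather than reversal

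*SAP*

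**What the plan says.** **Models.** In the SAP 5.14 model table, the reduced-model entry for Models 1, 2 and 3 is "None (intercept only model". The full model adds one term: an indicator for nadir below threshold in Models 1 and 2 (30 ng/mL for the direct inhibitors, 0.10 IU/mL for enoxaparin), or "Log of on-treatment Nadir" anti-fXa in Model 3. The decision rule is: "The Reduced Model will be rejected in favor of the Full Model if the Likelihood Ratio Test p-value is <0.05".

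**Exposure.** SAP 5.14 states the objective as the relationship of hemostasis to change from baseline, then argues that the level reached matters more: "Therefore, the on-treatment nadir value will be used in the analysis".

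**Covariates.** SAP 5.4 says: "No adjustment for covariates will be performed". Two models depart from that. Model 4 (ICH patients) includes "the log of (the baseline ICH volume + 1), and an indicator variable for baseline Infratentorial involvement", but neither baseline anti-fXa nor inhibitor. The mortality model in SAP 5.16.3 has age in both its reduced and full versions.

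**Adjusted analyses.** Protocol 11.5.7 says analyses adjusting for potential confounders will be performed: "Variables that may confound evaluation of a correlation between reversal of anti-fXa activity with effective hemostasis include anatomical location of bleeding", followed by mechanism and severity of injury, bleeding severity, interventions and hemostatic factors. SAP 5.15.1.11 repeats the list and then says: "These analyses will be defined later in an addendum to this analysis plan and will be labeled as post hoc".

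**Status.** SAP 5.7 treats secondary analyses as exploratory, without multiplicity adjustment. SAP 5.17.2 lists, among the changes in this version, pre-specification of the correlation of anti-fXa reversal with hemostasis.

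**The concern.** The crude comparison is fixed in advance, while the adjusted one has no model, no covariate coding and a post hoc label. SAP 1.0 refers to 477 patients already locked, so a later addendum would be written with those data in hand.

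Three things other than reversal could produce an association in Models 1–3.

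- **Baseline level.** A patient who starts higher needs a larger percentage fall to reach 30 ng/mL. SAP 5.3 says trials of the direct inhibitors show plasma concentration correlating with bleeding. SAP 5.5.1 tightens the link: if both on-treatment samples are missing, the nadir is set to baseline.
- **Inhibitor.** SAP 5.14 says activity levels cannot be combined across inhibitors, most of all between direct and indirect ones. Model 3 nevertheless pools continuous log nadir over apixaban, rivaroxaban and edoxaban with no inhibitor term. Edoxaban patients enter from 40 ng/mL, the other two from 75 ng/mL.
- **Bleed type.** Anatomical location heads the protocol's own list of confounders.

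Protocol 11.5.3 aims to establish anti-fXa change as a predictor of hemostasis. A positive likelihood-ratio test from a crude model would probably be cited as support for that.

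**Working it through.** **1. The plan's own figure.** The only stated design figure is 162 evaluable patients (61% against 50%, two-sided 0.05, 80% power). The score formula gives n = [(1.96·√(0.5·0.5) + 0.842·√(0.61·0.39)) / 0.11]² = 159.8, so 160. The exact binomial at n = 162 with success at 94 or more gives one-sided alpha 0.0246 and power 0.805. The figure reproduces but has no bearing on Models 1–3, for which no power is given.

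**2. How the nadir depends on baseline.** Nadir = baseline × residual fraction, so the fall needed to reach 30 ng/mL is 1 − 30/baseline.

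| Baseline (ng/mL) | Fall needed |
|---|---|
| 40 (edoxaban entry threshold) | 25% |
| 75 (apixaban, rivaroxaban entry threshold) | 60% |
| 150 | 80% |
| 300 | 90% |

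The same percentage reversal can thus fall on either side of the indicator, depending on where the patient started and on which inhibitor. In Model 3, log nadir = log baseline + log residual fraction. Without log baseline, the nadir coefficient mixes the two parts.

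**3. Simulation with no effect of reversal.** N = 477 × 0.70 × 0.95 = 317, using the planned 30% below threshold and 5% non-evaluable. The following are assumptions, not document figures: all patients on a direct inhibitor; log baseline = log 75 + |N(0, 0.9)|; median residual fraction 10% with log-SD 0.9; about 75% hemostasis; 65% ICH. Hemostasis depends on baseline level only. Each scenario has 1,500 runs with a likelihood-ratio test at 0.05. The adjusted versions carry log baseline and bleed type in both the reduced and full models.

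| Odds ratio for failure per SD of log baseline | Model 1 rejects | Model 3 rejects | Median Model 1 odds ratio | Adjusted, Models 1 / 3 |
|---|---|---|---|---|
| 1.0 | 5.9% | 5.2% | 0.99 | 6.3% / 5.1% |
| 1.25 | 11.5% | 14.6% | 1.23 | 5.3% / 5.4% |
| 1.5 | 28.7% | 43.6% | 1.49 | 5.5% / 4.9% |
| 2.0 | 67.1% | 84.9% | 1.96 | 4.9% / 4.7% |

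At N = 162, odds ratios of 1.5 and 2.0 give 17% and 40% (Model 1) and 24% and 58% (Model 3).

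**4. Sensitivity to baseline spread.** Here failure odds rise 1.25–2.0 per doubling of baseline, the median residual is 9% and N = 317. A baseline log-SD of 0.5–0.6 gives 6–27% (Model 1) and 6–40% (Model 3). A log-SD of 0.9 gives 13–69% and 17–85%. Median spurious Model 1 odds ratios run from 1.10 to 1.95. With baseline in both models, rejection is 4–7% throughout.

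**5. Bleed type alone.** Suppose bleed type carries an odds ratio of 1.5–3 and baseline differs by 0.5 log units between types. Model 1 then rejects in 6–12% and Model 3 in 7–15%. With no difference in level between types (odds ratio 2), the rates are 5.1% and 5.7%. Under other assumed rates a true odds ratio of 1 moved to between 0.72 and 1.13, so the bias can run either way.

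**The case against.** **The crude model answers a legitimate question.** Protocol 11.5.6 makes an unadjusted ROC curve the main tool, and SAP 5.14 deliberately takes the level reached as the exposure. Whether nadir predicts hemostasis, for whatever reason, needs no adjustment. Conditioning on baseline moves the question towards percent reduction. This stands as a reason to keep the crude models and the ROC. It does not make them sufficient, because SAP 5.14 states the objective as change from baseline and SAP 5.17.2 describes the analysis as one of reversal.

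**Baseline anti-fXa is not on the protocol's list.** True. A reader might infer that the SAP ignores a confounder the protocol named; for baseline level that is not so. The case for it rests on the arithmetic and on SAP 5.3.

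**Adjustment is deferred, not dropped.** Also true. The sample table list includes a summary of possible confounders (14.2.2.7), hemostasis by baseline anti-fXa (14.2.2.5a–c) and the effect of baseline characteristics in ICH (14.2.3.5). SAP 5.13 plans analyses by inhibitor, and 5.13.1.2 gives subgroups by bleed type. None of these defines an adjusted model, and the table list is said not to be updated.

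**The simulations build in the answer.** They assume that baseline acts on hemostasis other than through the nadir. If that effect is weak and the spread narrow, rejection is about 6%, which is negligible. They show what could happen, not what will.

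**Model 4.** A reader might infer that patients with subdural or subarachnoid bleeds drop out or enter with zero volume, because Protocol Appendix B rates those bleeds by thickness. The documents do not say so. SAP 4.5.9 takes hematoma volume from a case report form with an intracranial hemorrhage entry, and that form is not in the documents. What remains is that the SAP does not state how size enters for those compartments.

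**Conclusion.** The point holds as a gap in pre-specification with a real route to bias. Models 1–3 cannot separate reversal from baseline level, inhibitor or bleed type, and the adjusted analyses that could are undefined. With no effect of reversal, Model 1 rejects in roughly 6–69% of trials instead of 5%, and in about 4–7% once baseline is in both models. The width of that range reflects assumed baseline spread, residual fraction and baseline effect, none of which the documents give. It is illustrative, not a forecast for this trial. Bleed type matters less, and only if anti-fXa levels differ by bleed type.

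The documents do not support reading this as a flaw in the primary results. The analysis is secondary and exploratory, and no primary conclusion changes.

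**What to change.** - **Models 1–3 (SAP 5.14).** Pre-specify versions with log baseline anti-fXa (on an inhibitor-specific scale), bleed type (ICH, GI, other) and FXa inhibitor in both the reduced and full models. Keep the unadjusted models and the ROC as support, described as answering the purely predictive question.
- **SAP 5.15.1.11.** Define the remaining adjusted analyses before they are run.
- **SAP 5.4.** Limit the no-adjustment statement to the primary analyses, since Model 4 and the mortality model already adjust.
- **Model 4.** Add bleed compartment, and state how baseline size enters for subdural and subarachnoid bleeds.

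**Cost.** SAP wording. Baseline anti-fXa, inhibitor and bleed type are already collected, and thickness is already summarized under SAP 5.11.1. Model 1 gains six parameters (1 baseline + 2 bleed type + 3 inhibitor); Models 2 and 3 gain five. With N = 317, failures would number about 79 at 75% hemostasis (assumed; 0.25 × 317) or 124 at the planned 61% (0.39 × 317). That is about 11 to 18 failures for each of Model 1's seven slopes, which is workable. The adjusted estimate answers a slightly different question from the crude one, so the report should show both.

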5.16. Safety analysis

All safety analyses will be conducted using the Safety analysis population. Unless otherwise indicated, all analyses will be presented for an overall population (pooled across the different inhibitors) and stratified by the different inhibitors.

5.16.1. Extent of exposure

Drug exposure will be summarized by and exanet dose for the overall patient population and by FXa inhibitor, and by bleeding type. The number, percentage, exact 95% CI for percentage for the and exanet dose completed, modified, interrupted, and discontinued, and all treatment-emergent adverse events (TEAEs) that result on and exanet dose modification will be presented. In addition, the reason for drug modification, interruption, and discontinuation will be presented by patient as data listing.

In addition, patients that received re-dosing and the reason for re-dosing will be presented as data listing.

5.16.2. Adverse Events

A TEAE is defined as any AE that has an onset on or after the first dose of andexanet, or any pre-existing condition that has worsened on or after the first dose of andexanet. TEAEs will be attributed to andexanet using the following rules:

A treatment-related adverse event is defined as a TEAE possibly or probably related to and exanet. TEAEs with missing relationship will be counted as being treatment-related for analysis purposes.

The incidence of TEAEs, treatment-related AEs, TEAEs that led to early withdrawals, and serious AEs (SAEs) will also be summarized by maximum severity and most-related relationship to and exanet by MedDRA primary system organ class and preferred term. The summary will include the total number and percentage of patients reporting a particular event. In counting the number of events reported, a continuous event, i.e. reported more than once and which did not cease, will be counted only once; non-continuous adverse events reported several times by the

same patient will be counted as multiple events. AEs occurring prior to and examet treatment will be listed separately. Adverse events will be coded using MedDRA version 18.0.

Narratives of deaths, serious and other significant adverse events will be provided in the relevant section of the study report.

A complete patient listing of all adverse events will be provided in Appendix 16.2 to the study report. This listing will include treatment, AE verbatim, MedDRA primary system organ class and preferred term, the day of onset and cessation of event relative to first dosing of andexanet, duration of AE, whether serious (yes/no), severity, relationship to andexanet, action taken and outcome, treatment emergent and non-treatment emergent events will be listed separately.

AEs of special interest will be summarized. As defined in the protocol, AEs of special interest are thrombotic or embolic events of any severity, whether serious or not, and infusion reactions that are either serious or severe or both.

Adverse events will be summarized for the following subgroups of sex (male, female), race (any race with at least 5 members, all others combined), age deciles, and FXa inhibitor.

5.16.3. **Deaths**

All deaths will be assessed, and the causes of death adjudicated, by the EAC. Deaths due to cardiovascular causes (i.e., resulting from MI, sudden cardiac death, heart failure, stroke, CV procedures, CV hemorrhage, and other CV causes) will be classified as related to bleeding or non-hemorrhagic.

Kaplan-Meier curve for time to death will be presented by treatment by FXa inhibitor, and exanet dose, and and exanet manufacturing process. Patients who discontinue the study prior to Day 30 with an unknown survival assessment will be censored at the time of the last visit. Also, patients that completed the study (i.e., Day 30) will be censored at Day 30.

In addition, the proportion of patients that died during the 30 day follow-up with exact 95% CI will be presented for the overall safety population, by age category, region, FXa inhibitor, bleeding type, and exanet dose, and exanet manufacturing process, and by age deciles. In addition, the cause of death will be summarized.

The relationship between anti-fXa and 30-day mortality, will be analyzed (in the safety population), using a logistic regression model, with Age included as a covariate.

- 30-day mortality will define Death as Death at any time (including deaths recorded after Day 30). A sensitivity analysis defining Death as above (died during the 30 day followup) will be performed as well.
- Age will be entered into the model using a cubic spline transformation to best reflect the relationship with mortality.

- The Full Model will be compared to the Reduced Model with a Likelihood Ratio Test. The Reduced Model will be rejected in favor of the Full Model if the Likelihood Ratio Test p-value is <0.05.
 - Reduced Model: includes Age (with cubic spline transformation)
 - Full Model: includes Age (with cubic spline transformation) and an indicator variable for anti-fXa at on-treatment Nadir < threshold (where the threshold is 30 ng/mL for the DOACs, and 0.10 IU/mL for Enoxaparin).
- The area under the receiver operating characteristic (AUC under ROC) with the 95% CI will be presented for the Full Model.
- Descriptive statistics, odds ratios with the corresponding 95% confidence intervals, and p-values from the models will be presented also.

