2.4. Safety Objectives

- To evaluate the overall safety of and exanet including: adverse events, adjudicated Thrombotic Events (TEs) and deaths, vitals, clinical laboratory measurements, and antibodies to FX, FXa, and and exanet.
- To evaluate the 30-day all-cause mortality.

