4.3. Criteria for Discontinuation of Andexanet

And examet may be prematurely discontinued for a number of reasons, including:

- Any intolerable AE that cannot be ameliorated by appropriate medical intervention or that in the opinion of the Medical Monitor or Investigator would lead to undue risk if the patient were to continue on treatment.
- Withdrawal of consent. A patient may elect to withdraw consent to treatment or study participation at any time.

Patients who discontinue from the study after receiving any amount of and examet should undergo all follow-up safety procedures, unless the patient also explicitly withdraws consent for these procedures, in which case they should undergo an Early Termination visit.

Reasons for all withdrawals/discontinuations of andexanet will be recorded.

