5.3. Early Termination Visit

An early termination visit will be conducted if the patient is withdrawing from the study before the Follow-up Day 30 visit. Procedures at this visit will include the following:

- Record the reason for early termination.
- Record AEs since last study visit.
- Record use of concomitant medication since last study visit.
- Record dates of use of anticoagulant(s) on the anticoagulant CRF.
- Perform a final assessment of bleeding.
- Obtain a local laboratory Complete Blood Count (CBC).
- Collect central laboratory specimens for thrombin generation and antibodies (anti-andexanet, anti-fX, anti-fXa, and neutralizing antibodies).

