9.6. Adverse Event Reporting

The AE reporting period starts with the signing of the ICF and continues through the Follow-up Day 30 visit. Survival status and reason for death will be ascertained at 12 hours and at the Day 3 and Follow-up Day 30 study visits.

Patients in this study who experience an andexanet-related AE or SAE will be followed until the AE or SAE is resolved or until a new stable baseline is established, even if this occurs after the Follow-up Day 30 visit. All AEs spontaneously reported by the patient and/or in response to an open question from study personnel or revealed by observation, physical examination, or other diagnostic procedures will be recorded and reported on the appropriate CRF through Study Day 30.

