5.2. Analysis Populations

5.2.1. Safety Population

The Safety Population will consist of all patients treated with any amount of andexanet.

5.2.2. Efficacy Population

The Efficacy Population will include all patients in the Safety Population who meet all of the following criteria:

- Are determined by the EAC to meet the clinical bleeding inclusion criteria.
- Have a baseline anti-fXa level
- Baseline anti-fXa level of at least 75 ng/mL for apixaban and rivaroxaban, 40 ng/mL for edoxaban, and 0.25 IU/mL for patients receiving enoxaparin.

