5.16.4. Thrombotic Events

Potential Thrombotic Events (TEs) will be submitted by each Investigator for adjudication by the EAC using definitions pre-specified in the EAC Charter. The proportion of patients in the safety population who are adjudicated to have a TE by the independent EAC will be summarized. An exact 95% CI will be reported. Analysis will be performed for the safety patient population, by age category, sex, region, FXa inhibitor, bleeding type, andexanet dose, andexanet manufacturing process, medical history (i.e., atrial fibrillation (AF), Ischemic Stroke or Transient Ischemic Attack (CVA/TIA), Venous Thrombotic Event (VTE), or Cancer); and the type of TE (i.e., Ischemic Stroke (CVA), Myocardial Infarction (MI), Deep Vein Thrombosis (DVT), Pulmonary Embolism (PE), Arterial Systemic Embolism (ASE), and Transient Ischemic Attack (TIA). Also, the age, sex, FXa inhibitor, type of bleeding, previous history of TE, hospital length of stay and deaths for patients with and without thrombotic events will be compared.

An additional summary of possible TEs will be presented using a broader definition of TEs as recommended by FDA. See Section 4.6.8 for further details on the selection of events. The proportion of patients in the safety population who have a TE by this broader definition will be summarized. An exact 95% CI will be reported.

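### SAP 5.16.3 has no rule for unknown Day-30 survival in the mortality proportion: lost patients implicitly count as non-deaths there, yet are censored in the Kaplan-Meier curve

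*SAP*

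**What the plan says.** Protocol 2.4 lists as a safety objective "To evaluate the 30-day all-cause mortality", and SAP 2.4 repeats it.

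SAP 5.16.3 (Deaths) plans three mortality analyses:

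- **Proportion.** "the proportion of patients that died during the 30 day follow-up with exact 95% CI will be presented for the overall safety population", and also by age category, age decile, region, FXa inhibitor, bleed type, andexanet dose and manufacturing process. SAP 5.2.1 fixes the denominator: "The Safety Population will consist of all patients treated with any amount of andexanet".
- **Kaplan-Meier curve for time to death**, named for FXa inhibitor, dose and manufacturing process. Here the SAP does foresee missing status: "Patients who discontinue the study prior to Day 30 with an unknown survival assessment will be censored at the time of the last visit". Completers are censored at Day 30.
- **Logistic model** of 30-day mortality on on-treatment nadir anti-fXa, adjusted for age, in the safety population.

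Only the second has a rule for unknown survival. SAP 5.5, on dropouts and missing values, covers anti-fXa activity, hemostatic efficacy, NIHSS and ambiguous values, but not vital status.

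**The concern.** Within one section, the same patient is handled in two ways. In the curve the patient leaves the risk set. In the proportion the patient remains in the denominator and, with no death recorded, has the weight of someone alive on Day 30. The logistic model needs a yes or no for every patient and is silent on those for whom neither is known.

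This is a single-arm study, so the mortality percentage is read as an absolute safety figure, with no control arm in which a similar loss could offset it. Following the text literally moves the figure in one direction only: downward. The exact confidence interval reflects sampling error given the observed count and carries nothing for the unknown outcomes. For hemostatic efficacy, SAP 5.5.2 has a sensitivity analysis that classes every non-evaluable patient as a failure. Mortality has no counterpart.

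**Working it through.** **Who is affected.** Protocol 9.6 says: "Survival status and reason for death will be ascertained at 12 hours and at the Day 3 and Follow-up Day 30 study visits". Day 3 is thus the last scheduled check before Day 30. Protocol 5.2 allows unscheduled visits, and Protocol 5.3 adds: "An early termination visit will be conducted if the patient is withdrawing from the study before the Follow-up Day 30 visit". Either can fall between Day 4 and Day 29 and would then be the last visit. Censoring falls at Day 3 only for a patient with no such later visit. Under Protocol 4.3 and the Day-30 note in Appendix A, patients who discontinue keep the safety follow-up unless they withdraw consent to it. The affected group is therefore mainly those who withdraw that consent and those lost to follow-up, both listed as discontinuation reasons in SAP 4.1.1.

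**Which figures rest on the proportion alone.** Age, region and bleed type appear in the list for the proportion but not in the list for the curve. The general rule in SAP 5.16 could be read as adding a pooled curve. Even so, no Day-30 Kaplan-Meier estimate or interval is requested, so the overall mortality number is still the crude one.

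**Direction.** With d deaths among N treated, the crude figure is d/N. Kaplan-Meier passes the weight of each censored patient to those still at risk, so its Day-30 mortality is at least d/N. The two are equal when nobody is censored before the last death.

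**Size.** The documents give no mortality rate, loss rate or timing of deaths, so there is no stated figure to reproduce. Only N = 477 (SAP 1.0) is theirs; the rest is assumed.

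Illustration A: 72 deaths observed, 40% of them (28.8) by Day 3, L patients with unknown status, all censored at Day 3.

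- Crude: 72/477 = 15.1%
- Kaplan-Meier: 1 − (1 − 28.8/477) × (1 − 43.2/(477 − 28.8 − L))
- All unknowns dead: (72 + L)/477

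| L (share of 477) | Crude | Kaplan-Meier | All unknowns dead |
|---|---|---|---|
| 5 (1%) | 15.1% | 15.2% | 16.1% |
| 14 (3%) | 15.1% | 15.4% | 18.0% |
| 24 (5%) | 15.1% | 15.6% | 20.1% |

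Illustration B: mortality of 15% among patients with known status and 24 unknown, hence 68 deaths.

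- Unknowns kept as non-deaths: 68/477 = 14.3% (exact 95% CI 11.2% to 17.7%)
- Unknowns excluded: 68/453 = 15.0% (11.8% to 18.6%)
- Kaplan-Meier, with 20% to 40% of deaths before Day 3: 14.7% to 14.9% if censored at Day 3, 14.5% to 14.6% if censored at about Day 15
- All unknowns dead: (68 + 24)/477 = 19.3%

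In B the worst case lies above the upper limit of the crude interval (17.7%), so that interval does not cover what the losses could hide.

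**The case against.** The strongest reply is that a crude proportion and a Kaplan-Meier curve are complementary descriptive summaries, that no mortality hypothesis is tested, and that the gap between them is a fraction of a point. SAP 5.1 requires numbers of observations and events, and SAP 5.10.1 tabulates discontinuations and lists the reasons, so a reader could gauge the losses. Most of this stands, and it limits the size of the point. It does not supply the missing rule, and a count of discontinuations is not a count of unknown vital status.

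Four stronger readings are tempting, and the documents do not support them.

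- *That censoring never falls later than about Day 3.* The SAP censors at the last visit, scheduled or not, and early-termination or unscheduled visits can be later.
- *That the SAP instructs these patients to be counted as survivors.* It does not say so. That is the effect of an all-treated denominator with no rule.
- *That the early-termination procedures in Protocol 5.3 must be changed.* The list there has no later survival check, but under Protocol 4.3 the visit is for patients who have refused further follow-up procedures: "unless the patient also explicitly withdraws consent for these procedures, in which case they should undergo an Early Termination visit". Attendance also shows that the patient was alive that day. SAP 1.0 analyses 477 locked patients, for whom a new collection step comes too late.
- *That thrombotic events need a competing-risk analysis.* SAP 5.16.4 says: "The proportion of patients in the safety population who are adjudicated to have a TE by the independent EAC will be summarized". An all-treated denominator is conventional for adverse events, so cumulative incidence with death as a competing event is a preference here.

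One caution on dates also holds. SAP 4.6.6 imputes a missing discharge date and drops patients who withdrew consent from the length-of-stay analysis. An imputed discharge date is no evidence of survival.

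**Conclusion.** The point holds as a gap in the analysis rules of SAP 5.16.3. Patients with unknown Day-30 status implicitly count as non-deaths in the proportion, are censored in the curve, and have no rule in the logistic model. The direction is certain: the crude proportion is at or below the Kaplan-Meier value.

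The size cannot be fixed from the documents. With about 15% mortality and 1% to 5% unknown, both assumed, the crude figure is about 0.1 to 0.5 points below Kaplan-Meier when 40% of deaths occur by Day 3. At 5% unknown with fewer early deaths (20%, illustration B), the gap is about 0.6 points. The worst-case bound is about 1 to 5 points above the crude figure, but reaching it requires every unknown patient to have died. The likely effect is small. The change is still worth making because mortality is a stated objective and the remedy is cheap.

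**What to change.** In SAP 5.16.3:

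1. Report the number of patients with unknown Day-30 vital status, overall and in each listed subgroup.
2. Present Kaplan-Meier Day-30 mortality with a 95% CI, overall and for every subgroup now listed for the proportion, with the crude proportion alongside.
3. Censor at the last date on which the patient is actually recorded as alive (any visit, or a recorded discharge, laboratory or other dated entry), never at an imputed date.
4. Add a sensitivity analysis that counts unknowns as deaths, parallel to the one for hemostatic efficacy in SAP 5.5.2.
5. State the same unknown-status rule for the mortality logistic model.

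The cost is a few sentences in the SAP and some programming on dates already collected. No protocol change is needed. The downside is that the stated mortality may be slightly less favourable.
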